4.2 Dose Limiting Criteria and Maximum Tolerated Dose

4.2.1 Dose Limiting Criteria

Dose limiting toxicity, if observed, will be declared by the SRC, based on their review of the relevant clinical information.

Determination of dose limiting toxicity will include consideration of the following events:

- 1. Ocular inflammation increases by 2 units from pre-injection on the Standardization of Uveitis Nomenclature (SUN) grading scale for aqueous cell or vitreous haze, secondary to inflammation and not the drug formulation itself, identified post-injection of ONL1204 and prior to retinal reattachment surgery;
- 2. Sustained elevation of IOP characterized as > 30 mmHg for 3 consecutive days, postinjection of ONL1204 and prior to retinal reattachment surgery, despite pharmacologic therapy;
- 3. Reduction in visual acuity from baseline after injection of ONL1204 and prior to retinal reattachment surgery, that in the opinion of the investigator is likely due to the investigational product and results in a:
 - a) Decrease in visual acuity from 20/200 or 20/400 to light perception without progression of the underlying retinal detachment; or
 - b) Decrease in visual acuity from baseline to no light perception.
- 4. Any serious adverse event (SAE) that occurs within the first 14 days following ONL1204 injection that, in the opinion of the investigator, is related to ONL1204.

Page 23 of 52

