4.3 Schedule of Assessments

Table 4-1 Schedule of Study Procedures and Assessments

Study Visit	Visit 1 Day 1 Baseline ² / Injection			Visit 2 Day 2 (¹ ,	Visit 3 (Day 4 +)	Visit 4	Visit 5	Visits 6, 7	Visit 8	Unscheduled Visit(s)
				1 day Post- Injection	3 + days Post- Injection) Day of Surgery (Vitrectomy) ³	1 Day Post- Surgery	14 Days (±4 days) Post- Surgery	Weeks 6, 9 (±7 days)	Week 24 (±14 days) Exit or early termination	
Assessment	Pre- Injection	Study Drug IVT	Post- Injection							
Informed Consent	X									
Medical History	X									
Demographics	X									

³ All Visit 3 procedures are to be performed before vitrectomy.

Note: Screening procedures are in red.

Abbreviations: AE = Adverse event; ETDRS = Early Treatment Diabetic Retinopathy Study; IOP = Intraocular pressure; PK = Pharmacokinetic;

Post-op = Postoperative; OU = Both eyes; SD OCT = Spectral Domain Optical Coherence Tomography; SE = Study eye; UA = Urine analysis.

¹ IOP > 30 mmHg requires consecutive daily visits until resolved or vitrectomy. Visits between visit 2 and 3 may be added per investigator's discretion.

² All baseline procedures to be done before injection, except blood draw for ONL1204 levels and PK sample (may be drawn with clinical laboratory evaluations, and 1 hour [\pm 15 minutes] after injection), and AE reporting, (pre- and post-injection). If injection is scheduled for early morning, baseline procedures can be done the day before surgery.

Page 25 of 52

Study Visit	Visit 1 Day 1			Visit 2 Day 2 (¹ ,	Visit 3 (Day 4 +)	Visit 4	Visit 5	Visits 6, 7	Visit 8	Unscheduled Visit(s)
	Bas	eline ² / Inje	ction	1 day Post- Injection	3 + days Post- Injection) Day of Surgery (Vitrectomy) ³	1 Day Post- Surgery	14 Days (±4 days) Post- Surgery	Weeks 6, 9 (±7 days)	Week 24 (±14 days) Exit or early termination	
Assessment	Pre- Injection	Study Drug IVT	Post- Injection							
Concomitant Medications	X			X	X	Х	X	X	Х	Х
Vital Signs	X			X	Х	Х	X	Х	Х	Х
Height and weight	Х									
Pregnancy Test (UA) (females only)	X								Х	
ETDRS Best Corrected Visual Acuity	OU			OU				OU	OU	SE ⁴
Clinical Laboratory Evaluation	X		X		X				X	

Note: Screening procedures are in red

Abbreviations: AE = Adverse event; ETDRS = Early Treatment Diabetic Retinopathy Study; IOP = Intraocular pressure; PK = Pharmacokinetic; Post-op = Postoperative; OU = Both eyes; SD OCT = Spectral Domain Optical Coherence Tomography; SE = Study eye; UA = Urine analysis. ⁴ OU if clinically indicated.

Page 26 of 52

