6.4 Study Procedures and Assessments

6.4.1 Study Visits

There is a minimum of 10 scheduled study visits:

- Visit 1: Day 1 (baseline/injection)
- Visit 2: Day 2 (1day post-injection)
- Visit 3: Day of Vitrectomy (3 + days post-injection in accordance with standard of care)
- Visit 4: Postoperative visit (1 day post-surgery)
- Visit 5: Clearance of sentinel patient/cohort Day 14 (+4 days) post-surgery
- Visit 6: Week 6 (±7 days)
- Visit 7: Week 9 (±7 days)
- Visit 8: Week 24/Exit (±14 days)

Patients may return for a non-scheduled visit at any time if deemed appropriate by the investigator.

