9.3.1.4 BCVA

BCVA will be summarized using descriptive statistics for each treatment group for all time points assessed, including change from baseline for all post-treatment assessments. BCVA assessment will be split between the study eye and fellow eye.

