For PK concentration data, the number of non-missing values, number of below limit of quantification (BLQ) values, arithmetic mean, standard deviation, median, minimum, maximum, coefficient of variation (CV%), geometric mean and geometric coefficient of variation (geo CV%) values will be presented. For the calculation of summary statistics, unrounded data will be used and reported to three significant figures except for n, n BLQ, and CV% which will be presented to the nearest integer and one decimal place, respectively.

For PK parameters data, the number of non-missing values, arithmetic mean, standard deviation, median, minimum, and maximum values will be presented. Individual PK parameters will be presented to three significant figures except for T_{max} which will be presented to two decimal places.

- Categorical variables: Descriptive statistics will include counts and percentages per category. The denominator in all percentage calculations will be the number of participants in the relevant analysis population with non-missing data, unless specifically stated otherwise. Percentages will be displayed to one decimal place. Proportions will be displayed to 3 decimal places.
- Unscheduled assessments: Only values collected at scheduled study visits/time points will be presented in summary tables. If a repeat assessment was performed, the result from the original assessment will be presented as the result at the specific visit/time point. All collected data will be included in the data listings.

- Assessment windows: All assessments will be included in the data listings and no visit windows will be applied to exclude assessments that were performed outside of the protocol specified procedure windows.
- Result display convention: Results will be center aligned in all summary tables and listings. Participant identifiers visit and parameter labels may be left-aligned if required.
- Date and time display conventions: The following display conventions will be applied in all outputs where dates and/or times are displayed:

Date only: YYYY-MM-DD

Date and time: YYYY-MM-DD HH:MM

If only partial information is available, unknown components of the date or time will be presented as 'NK' (not known), i.e., '2016-NK-NK'. Times will be reported in military time.

Key Definitions

The following definitions will be used:

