- Baseline: The baseline value is defined as the last available valid (quantifiable continuous or categorical value), non-missing observation for each participant prior to first study drug administration. Repeat and unscheduled assessments will be included in the derivation of the baseline values.
- Change from Baseline: The change from baseline value is defined as the difference between the result collected/derived at a post-baseline visit/time point and the baseline value.

The change from baseline value at each post-baseline visit/time point will be calculated for all continuous parameters using the following formula:

Change from Baseline Value = Result at Visit/Time Point – Baseline Value

The change from baseline value will only be calculated if the specific post-baseline visit/time point result and the baseline value for the parameter are both available and will be treated as missing otherwise.

• Study day: The study day of an event is defined as the relative day of the event starting with the date of the first study drug administration (reference date) as Day 1 (there will be no Day 0).

The study day of events occurring before the first study drug administration will be calculated as:

Study Day = (Date of Event - Date of First Study Drug Administration)

For events occurring on or after Day 1, study day will be calculated as:

Study Day = (Date of Event - Date of First Study Drug Administration) + 1

Study days will only be calculated for events with complete dates and will be undefined for events that are 'Ongoing' at the end of the study.

Relative days compared to an alternative reference point will be calculated similarly, but the alternative starting reference start date will be used instead of the date of the first study drug dosing.

- Prior Medications: Prior medications are defined as any medication where the use was stopped prior to the first administration of the study medication.
- Concomitant Medications: Concomitant medications are defined as any medication (other than the study drug) that was used at least once after the first administration of the study drug. Medications that were stopped on the same date as the first study drug administration will be defined as concomitant medications. If a clear determination cannot be made (partial medication end dates) the medication will be classified as concomitant.

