15. CHANGES TO THE PLANNED ANALYSIS

Not Applicable

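### Acuity readings taken at added visits between Day 2 and vitrectomy cannot enter the SAP's BCVA summary tables, which leaves a reporting gap in a primary safety endpoint

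*SAP*

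**What the plan says.** SAP 3 (Unscheduled assessments) states: "Only values collected at scheduled study visits/time points will be presented in summary tables". Everything else goes to listings: "All collected data will be included in the data listings". SAP 13.1.5 summarises BCVA by visit in letters and logMAR. It does not override the general rule and plans no worst-value summary.

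Protocol 9.3.1.4 describes the BCVA summary as "for all time points assessed, including change from baseline for all post-treatment assessments". SAP 15, on changes to the planned analysis, reads "Not Applicable".

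Extra visits are expected. Table 4-1, footnote 1, says: "Visits between visit 2 and 3 may be added per investigator's discretion". Protocol 6.4.1 adds: "Patients may return for a non-scheduled visit at any time if deemed appropriate by the investigator". The Unscheduled column of Table 4-1 includes ETDRS BCVA for the study eye, or both eyes if clinically indicated.

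BCVA is named among the primary safety endpoints (protocol 3.1 and SAP 2.1.4). The third dose-limiting criterion in protocol 4.2.1 concerns "Reduction in visual acuity from baseline after injection of ONL1204 and prior to retinal reattachment surgery".

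**The concern.** The days between injection and vitrectomy are when an acuity change is least mixed with the effect of surgery, and the dose-limiting acuity criterion refers to those days. If no scheduled BCVA falls there after Day 2, a reading that documents a loss can exist only at an added visit, and the SAP rule keeps it out of the cohort summaries. A reader comparing doses from Tables 14.3.6.1 and 14.3.6.2 could then see no pre-surgery change in a cohort where one eye lost substantial vision. The next tabulated value is Week 6, after surgery has altered the vision being measured. The TEAE tables would show that an event occurred and how severe it was, but not how much acuity was lost.

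**Working it through.** The plan gives no sample size, power or effect figure to reproduce. The check reads the schedule, applies the SAP rule, and then sizes an illustrative event.

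**1. ETDRS BCVA row of Table 4-1**

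| Column | ETDRS BCVA |
|---|---|
| Visit 1, pre-injection | both eyes |
| Visit 2 (Day 2) | both eyes |
| Visit 3 (day of surgery) | none |
| Visit 4 (1 day after surgery) | none (pinhole acuity only) |
| Visit 5 (14 days after surgery) | none |
| Visits 6 and 7 (Weeks 6 and 9) | both eyes |
| Visit 8 (Week 24) | both eyes |
| Unscheduled | study eye; both if indicated |

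The column alignment was checked against other rows. The pinhole row falls at Visit 4, which agrees with SAP 13.1.11.

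- Scheduled BCVA readings after injection and before surgery: 1 (Day 2).
- Scheduled BCVA readings after Day 2 and before surgery: 0.

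**2. Applying SAP 3.** Every BCVA reading in that second interval is unscheduled, so it goes to Listings 16.2.11.1 and 16.2.11.2 and to neither BCVA table.

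**3. How much of the interval is affected.** Let s be the days from injection to surgery, with the Day 2 test one day after injection. The share of the interval after that test is (s − 1)/s. Assume s from 3 (the minimum in protocol 4.1) to 7 (the clinical plan in protocol 1.2.1).

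- s = 3: 2/3 = 67%
- s = 7: 6/7 = 86%

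These are shares of time, not of risk.

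**4. Size of an omitted reading.** SAP 13.1.5 codes hand motion (HM) as 3.0, light perception (LP) as 3.9 and no light perception (NLP) as 4.0 logMAR. On the Snellen scale 20/100 is log10(5) = 0.70, 20/200 is log10(10) = 1.0, and 20/400 is log10(20) = 1.30. Assume a cohort of 4, one eye falling at an added visit, and no change in the other three. The mean worst-value change is (worst − baseline)/4.

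| Fall | Change in the eye | Cohort mean change |
|---|---|---|
| 20/200 to LP | 3.9 − 1.0 = +2.9 | +0.725 |
| 20/400 to LP | 3.9 − 1.3 = +2.6 | +0.65 |
| HM to NLP | 4.0 − 3.0 = +1.0 | +0.25 |
| 20/100 to NLP | 4.0 − 0.7 = +3.3 | +0.825 |

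The last two rows span the permitted entry acuity (inclusion criterion 4). In each case the reading contributes nothing to the planned BCVA tables.

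**The case against.** The strongest reply is that nothing is hidden. Protocol 7.11 makes a decrease in acuity an adverse event, so a relevant loss appears in the ocular TEAE tables by severity and by relationship to drug and procedure. The listings give each reading in letters and logMAR, and with 4 patients per cohort they are short. No hypothesis is tested. This stands, and it limits the point to presentation. It does not remove it, because no cohort summary would show the size of a pre-surgery loss.

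Four stronger readings are tempting, and the documents do not support them.

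- **That the eye drops out of the BCVA summaries.** It does not. Its baseline, Day 2 and Week 6, 9 and 24 values still count; only the extra reading is left out.
- **That the omission always favours the drug.** This is not shown. Table 4-1 footnote 1 also requires daily visits for IOP above 30 mmHg, and other visits are discretionary, so some omitted readings may show stable or better acuity. Nor is the baseline rule ("Repeat and unscheduled assessments will be included in the derivation of the baseline values") evidence of one-sidedness, since it takes the last valid pre-dose value.
- **That dose escalation or the MTD is compromised.** Under protocol 4.2.1 and 10.2 the SRC judges toxicity from clinical data during the study. Under protocol 9 the database for these tables is created only after all patients have finished or discontinued.
- **That the slit-lamp summaries share the gap.** That row of Table 4-1 has lost its column positions in the text available, so no such claim can be made.

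The conflict with protocol 9.3.1.4 is also arguable. Its wording can be read, with protocol 9.3, as meaning nominal time points, and a discretionary visit has no common time point to average over. On that reading SAP 15 is not wrong, though the restriction is still worth stating.

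**Conclusion.** The point holds as a reporting gap. Under SAP 3 and Table 4-1, no BCVA reading after Day 2 and before vitrectomy can enter Tables 14.3.6.1 or 14.3.6.2. The effect is likely to understate acuity loss, because added visits are made when the investigator thinks them appropriate, but the direction is not certain.

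The illustrative cohort mean shift runs from +0.25 to about +0.83 logMAR. It assumes one event in four eyes, seen only at an added visit, with the other eyes unchanged. It compares a worst-value statistic with a by-visit table, so it measures what the planned display cannot show and does not estimate bias in any planned mean. The documents give no event rate from which to estimate how often this would happen. The improvement is worth making because it is cheap and concerns a primary safety endpoint; the trial's safety oversight does not depend on it.

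**What to change.** Keep the by-visit BCVA tables on scheduled visits, and make three changes to the SAP.

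1. Add to Tables 14.3.6.1 and 14.3.6.2, by cohort and for each eye, the worst post-injection BCVA per patient and its change from baseline. Use all scheduled, unscheduled and repeat readings, and show injection to vitrectomy separately from after vitrectomy.
2. Footnote the number of assessments per patient, and state that the row neither attributes cause nor accounts for progression of the detachment. Criterion 3 depends on likely drug causality, and its part (a) on absence of progression, so this row must not be read as a count of dose-limiting events.
3. State in SAP 15 that by-visit summaries are limited to scheduled visits, since protocol 9.3.1.4 can be read as covering every post-treatment assessment.

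The cost is some SAP wording and one block of rows in each of two existing tables, from data already collected. No trial procedure changes. The downside is that a worst value is the extreme of several readings, so patients seen more often will tend to look somewhat worse; the footnoted counts let the reader allow for this.

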4.1 Overview of Study Design

Sixteen patients will be enrolled in 4 ascending dose groups.

After signing informed consent and meeting all eligibility criteria, patients will undergo a vitreous tap for cytokine and other potential molecular biomarker analysis followed by a single intravitreal injection of ONL1204. This will occur on the day of diagnosis (Day 1). Safety visits will be conducted 1 day post-injection and per Investigator's discretion until Visit 3. At Visit 3 (3+ days post-injection, in accordance with standard of care) patients will undergo surgical repair of their retinal detachment with vitrectomy (with or without scleral buckling) and gas or oil tamponade. At the time of surgery, an undiluted vitreous sample will be collected for pharmacokinetic and pharmacodynamics analyses, and an aqueous sample will be collected for pharmacodynamic analysis. Additional safety visits will be conducted 1 day post-surgery, 14 (+4 days) days post-surgery, Weeks 6, 9 (\pm 7 days each), and Week 24 (\pm 14 days; study exit).

As this is a first-in-human safety study of ONL1204, the first patient in the first cohort will receive the lowest dose of ONL1204. After this patient completes Visit 5 (14 +4 days post-surgery) and a safety review committee reviews the data, the remainder of the patients in that cohort will be enrolled. After all patients in the cohort have completed Visit 5, the SRC will review the available safety data to determine if dose

limiting toxicity exists that prohibits enrolling the next higher dose cohort. This process will be repeated until escalating to the top dose.

The following doses will be evaluated: $25 \ \mu g$, $50 \ \mu g$, $100 \ \mu g$, and $200 \ \mu g$ ONL1204. ONL1204 is available in vials with concentrations of 0.5 mg/mL and 2 mg/mL. Therefore, a volume of 0.05 or 0.1 mL will be injected into the study eye.

Patient participation will be approximately 24 weeks (6 months): a single injection treatment and 24 weeks of follow-up.

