6.4.2 Study Procedures

Refer to the Schedule of Assessments (Table 4-1) for the timing of procedures. Additional details are provided as necessary in the manual of procedures (MOP), and in the sections that follow. A list of study procedures for this study is below:

- Vital signs
- Height and weight
- Clinical laboratory evaluation
- ETDRS BCVA at 3 meters
- Pin Hole Visual Acuity
- Low Luminance BCVA at 3 meters
- Low Contrast BCVA (2.5%)
- Contrast Sensitivity using the Muenster Aging and Retina Study (MARS) system
- Farnsworth D15 Color Vision Test
- Intraocular Pressure
- Slit Lamp Biomicroscopy
- Indirect Ophthalmoscopy
- Fundus photography
- Fundus autofluorescence
- Spectral Domain Optical Coherence Tomography (SD OCT)
- B scan ultrasonography of the affected eye with measurement of the height of detachment at the macula (this assessment is optional)
- Plasma ONL1204 levels
- Vitreous tap for inflammatory cytokine and other potential molecular biomarker analysis at baseline (post-injection) and vitreous sampling (non-diluted) for cytokine

and other potential molecular biomarker analysis and ONL 1204 levels at time of vitrectomy

- Anterior chamber fluid (tap) for cytokine and other potential molecular biomarker analysis, and ONL1204 levels at baseline and at the time of vitrectomy
- Injection of ONL1204
- Urine pregnancy test (females of childbearing potential only)

Additional Procedure:

• Standard of care vitrectomy (with or without scleral buckling) with gas tamponade

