8 ADVERSE EVENTS

8.1 Pretreatment Event Definition

A pretreatment event is any untoward medical occurrence before administration of any study medication or study procedure in a patient or subject who has signed informed consent to participate in a study; it does not necessarily have to have a causal relationship with study participation.

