9.3.1.1 Adverse Events

Adverse events will be coded to a Medical Dictionary for Regulatory Activities (MedDRA) preferred term and system organ classification. The occurrence of treatmentemergent AEs will be summarized using MedDRA preferred terms, system organ classifications, and severity. TEAEs are defined as adverse events that occurred or worsened following the first administration of study medication. Separate summaries of treatment-emergent SAEs and TEAEs considered related to study treatment and AEs leading to study treatment discontinuation will be generated. All AEs will be listed for individual patients showing both verbatim and preferred terms.

Ocular and systemic AEs will be reported separately. Ocular AEs will be split into study eye and fellow eye events. Events reported in 'both' eyes will be counted in the study and fellow analysis. Separate causality analyses will be performed for the study eye events (related to drug and related to procedure); for fellow eye and systemic events, causality will be assessed based on study drug alone.

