- Actual Time from First Dose (hours) = (Date/Time of First Dose PK Sample collection) (Date/Time of First Dose)
- Actual Time Deviation (hours) = (Actual PK Sample Collection Time Post Dose) (Scheduled PK Sample Collection Time Post Dose).
- Treatment Emergent Adverse Events (TEAEs) are defined as adverse events that occurred following the first administration of study medication.

Inferential Analyses

Descriptive statistics will be used to summarize the safety, PD and PK data. No formal hypothesis testing is planned.

Multiple Comparisons and Multiplicity Adjustments.

Not applicable for this study.

Handling of Missing Data

For the classification of Treatment emergent adverse event (TEAE) and Concomitant medication, the following will be applied in the following order:

- a. If all dates/times (start and stop) missing, the event/medication will automatically be classified as a TEAE/Concomitant medication.
- b. For AEs with a missing start date/time, if the event end date/time is prior to first study drug administration, the event will not be classified as a TEAE.
- c. If only the AE start year/ medication end year is present and is the same or is after the first study drug administration year unit, the event/medication will be classified as a TEAE/Concomitant medication.
- d. If the AE start month and year/medication end month and year are present and are the same or after the first study drug administration month and year units, the event/medication will classified as a TEAE/Concomitant medication.

For plasma concentration-time data/profiles and PK analysis the following will be applied:

- a. Concentrations that are below limit of quantification (BLQ) prior to the dosing (Pre-dose) will be set equal to zero. Post dose BLQ concentrations will be set to zero.
- b. Where there are no results, these will be set to missing.
- c. If more than 75% of values per nominal timepoint and treatment group are BLQ, then all descriptive statistics, except for nBLQ, will be denoted as not calculable (NC).
- d. For the purpose of calculating the non-compartmental plasma PK parameters, concentrations that are BLQ prior to the first quantifiable value will be set equal to zero and BLQ values after measurable concentrations will be set to zero.
- e. For the calculation of summary statistics of plasma PK parameters, all NR (not reported) and NC (not calculable) values in a data series will be set to missing.

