11. PHARMACODYNAMICS

Pharmacodynamic statistical analyses will be conducted based on the proteomic analysis of cytokine biomarkers in ocular fluids.

The following PD endpoints will be assessed:

- Vitreous Humor sample collected at pre-injection baseline by vitreous tap
- Vitreous Humor sample from the undiluted sample collected at the time of surgery
- Aqueous Humor sample collected at the time of surgery

Analyte concentrations will be provided for the vitreous humor and aqueous humor samples.

All PD endpoints will be analyzed separately by ONL Therapeutics.

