13.1.1 Adverse Events

All AEs will be coded using MedDRA. All AE summaries will be restricted to TEAEs only. Summary tables will include the number of participants (%) experiencing an event and the number of events. Participants will be counted only once for each SOC and PT level (categorical descriptive analysis).

Ocular and non-ocular AEs will be reported separately. Ocular AEs will be split into study eye/fellow eye/Both eye events.

The TEAE summaries will include:

- Overall summary of TEAEs.
- TEAE summary by SOC and PT.
- TEAE summary of serious adverse events (SAE) by SOC and PT.
- TEAE summary by SOC, PT and Severity.
- TEAE summary by SOC, PT, and relationship to study drug.
- TEAE summary by SOC, PT, and relationship to procedure.
- TEAE summary of events leading to the study drug removal by SOC and PT.

All listings will be presented by the safety population. Separate listings will be provided for patients with SAEs, AEs leading to withdrawal from the study and AEs resulting in death, if any.

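### The SAP omits worsening from the TEAE definition and puts both-eye adverse events in a class of their own, contrary to protocol 9.3.1.1 and undeclared in SAP 15, so some adverse-event counts can fall below what the protocol's rules give

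*SAP*

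**What the plan says.** **Worsening.** Protocol 9.3.1.1 says that "TEAEs are defined as adverse events that occurred or worsened following the first administration of study medication". The SAP, under Key Definitions in section 3, says that "Treatment Emergent Adverse Events (TEAEs) are defined as adverse events that occurred following the first administration of study medication". The sentences are almost identical, but the SAP leaves out worsening. SAP 13.1.1 then adds: "All AE summaries will be restricted to TEAEs only".

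**Both-eye events.** Protocol 9.3.1.1 splits ocular AEs by study eye and fellow eye, and counts an event reported in both eyes in each of the two analyses. It also asks for separate study-eye causality analyses, one for drug and one for procedure. SAP 13.1.1 splits ocular AEs into three classes: study eye, fellow eye and both eyes. It does not say that events in the third class are added to the other two.

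**Declared changes.** SAP 15, the section for changes to the planned analysis, reads Not Applicable.

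**The concern.** AE reporting is the first of the primary endpoints (protocol 3.1 and 9.2.1). A reader of the final tables will assume that treatment-emergent and study-eye counts follow the protocol. If they follow the SAP, some rows can show a lower incidence, or a lower maximum severity, with no notice that the rule changed.

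The usual safeguard would not catch this. SAP 16 bases the final analysis on the SAP and sends departures from the planned analysis to the study report. A programmer who follows the SAP exactly has no departure to report. Protocol 9.3 leaves to the SAP the patient populations and the handling of missing, unused and spurious data. It does not mention redefining treatment emergence.

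**Working it through.** The documents give no sample size, power or event-rate figure on this point, so there is nothing to reproduce. The check compares the texts and then counts directly.

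**Step 1. Can an AE start before the dose?** Yes.
- Protocol 8.1 limits a pretreatment event to "any untoward medical occurrence before administration of any study medication or study procedure". From the first study procedure onward, an event is an AE.
- Protocol 4.1 says that "patients will undergo a vitreous tap for cytokine and other potential molecular biomarker analysis followed by a single intravitreal injection of ONL1204", and SAP 11 lists a "Vitreous Humor sample collected at pre-injection baseline by vitreous tap". Table 4-1 also places the tap in the pre-injection column.
- Footnote 2 to Table 4-1 provides for "AE reporting, (pre- and post-injection" (closing bracket omitted), so such an AE would be collected.
- Protocol 6.4.2 differs: "Vitreous tap for inflammatory cytokine and other potential molecular biomarker analysis at baseline (post-injection" (closing bracket omitted). If that timing applied, an AE at the tap would be post-dose and would count under both definitions. The passages need reconciling. Other baseline procedures, such as the blood draw, still precede the injection.

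**Step 2. What happens to it?** Suppose the AE has a recorded onset before the injection, worsens after ONL1204 and is kept as one record. It is treatment-emergent under the protocol and not under the SAP. The SAP's missing-date rules use start and end dates and have no severity-change date, so they do not bring it back. An ocular AE of this kind would be absent from Tables 14.3.3.1, 14.3.3.2, 14.3.3.4, 14.3.3.5 and 14.3.3.6 in SAP 18, which is 5 tables. If serious, it would also be absent from 14.3.3.3, making 6.

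**Step 3. Both rules on an invented cohort.** Take 4 patients: one with a post-dose study-eye AE, one with a post-dose both-eye AE, one with a study-eye AE that began before the dose and worsened after it (one record), and one with none. The SAP's three classes are read as mutually exclusive.

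| Row | Protocol rule | SAP rule |
|---|---|---|
| Study eye | 3/4 = 75% | 1/4 = 25% |
| Fellow eye | 1/4 = 25% | 0/4 = 0% |
| Both eyes | no separate row | 1/4 = 25% |
| Any ocular TEAE | 3/4 = 75% | 2/4 = 50% |

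The both-eye patient accounts for 25 points of the study-eye difference and all of the fellow-eye difference. The worsened event accounts for the other 25 study-eye points and the whole difference in the ocular total. The both-eye class alone leaves that total unchanged.

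**Step 4. Weight of one patient.** This assumes that the patient has no other event in the row.
- Planned cohort: 1/4 = 25 points. All cohorts: 1/16 = 6.25 points.
- If one injected patient is replaced and stays in the Safety population: 1/5 = 20 points and 1/17 = 5.9 points.

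**The case against.** The strongest reply on worsening is that the protocol already handles it upstream. Protocol 8.2 makes a previous condition that has increased in severity or frequency since dosing an AE in its own right. Protocol 7.11 treats clinically relevant deterioration the same way, including a fall in visual acuity or a persistent rise in IOP. A worsening entered as a new record has a post-dose start, and the SAP definition captures it. This stands, and it makes the gap narrow. It does not close the gap, because the documents do not say that sites must open a new record, and the eCRF conventions are not given. Protocol 7.11 also prefers one comprehensive event for signs and symptoms of a common pathology. The SAP's missing-date rules lean towards treatment emergence, which narrows the gap further, but an onset with a recorded time before the injection is still excluded.

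On both-eye events, the SAP never says that they are left out of the single-eye counts, and the table titles in SAP 18 say only ocular or non-ocular. That also stands. The low counts follow only where the eye split is shown and the classes are treated as exclusive. SAP 13.1.1 and 18 do provide ocular summaries by relationship to drug and to procedure. A reader might infer that study-eye causality rows will be understated, but no listed table title shows such rows and no shells are given. If a both-eye row is printed, event counts can be added back. Participant counts cannot always be, because one patient may have both kinds of event.

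The SAP's references cite protocol version 1.6. The title page of the supplied protocol was removed, so a version match could not be confirmed.

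**Conclusion.** The point holds as a minor one. SAP section 3 and SAP 13.1.1 depart from protocol 9.3.1.1 on two AE-counting rules for a primary endpoint, and SAP 15 declares neither. Confidence is high on the mismatch in wording and medium on its consequences.

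The number of patients affected is unknown and may be 0. The percentages above are the weight of one patient in small denominators, not evidence that any count will be wrong. The first departure matters only for AEs that start before the dose, worsen after it and stay one record. The second matters only where the eye split is displayed without adding both-eye events to each eye.

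A reader might infer more than this:
- That events are lost. They are not: AE listing 16.2.7.1 is not restricted to TEAEs, and both-eye events remain in the ocular totals.
- That inference is compromised. Protocol 9.1.1 and the SAP's section on inferential analyses plan no formal hypothesis test.
- That dose escalation or the MTD decision was affected. The safety review committee reviews available safety data during the study (protocol 4.1 and 10.2), and nothing ties those reviews to the SAP's TEAE tables.

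**What to change.** In the SAP, before database lock:

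1. Define TEAEs as AEs that occurred or worsened after the first administration. Add a convention that a post-dose worsening is entered as a new record or carries a severity-change date.
2. State that both-eye events count in both the study-eye and the fellow-eye summaries, including those by relationship to drug and to procedure. A both-eye row may be kept for information.
3. If either SAP rule is intended, declare and justify it in SAP 15 instead.

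The sponsor should also confirm that the protocol being compared is version 1.6.

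The cost is SAP wording and the matching programming, from data already collected. No visits or assessments are added. If the eCRF holds no severity-change date, the worsening rule needs a data-entry convention agreed before lock.
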